8.2.2.2 Dermatology Life Quality Index (DLQI)

[figure not shown]
The DLQI is a subject-reported quality of life index which consists of 10 questions concerning symptoms and feelings, daily activities, leisure, work, school, personal relationships, and treatment during the last week. Each question is scored on a scale of 0 to 3 where 0="not at all", 1="a little", 2="a lot", or 3="very much". The scores are summed, giving a range from 0 (no impairment of life quality) to 30 (maximum impairment). Question 7 includes 2 questions, if the subject answers 'Yes' to Q7, the score given is a 3. If the subject answers 'No' to Q7, they are asked the second question where a score of 0="not at all", 1="a little", or 2="a lot" is given. Certain questions include an option for not relevant. When scoring, any questions deemed 'not relevant' will take on a value of 0.

. Interpretation of DLQI scores is as follows:

1. 0-1 = no effect at all on patient's life
2. 2-5 = small effect on patient's life
3. 6-10 = moderate effect on patient's life
4. 11-20 = very large effect on patient's life
5. 21-30 = extremely large effect on patient's life

Individual scores for each question will be provided by the eCOA system. The DLQI score will be derived in the analysis datasets.

Sponsor: Bristol-Myers Squibb
Protocol no: IM011065

8.2.2.8 Psoriatic Arthritis Screening and Evaluation (PASE) Questionnaire

The PASE questionnaire will be administered at Screening in subjects with peripheral joint complaints. The PASE questionnaire is a self-administered tool that is used to screen for psoriatic arthritis among subjects who have psoriasis. The PASE questionnaire consists of 15 questions subdivided into 7 questions focusing on symptoms of psoriatic arthritis, and 8 questions focusing on the impact of psoriatic arthritis on function. Each question is scored on a 1 to 5 scale, with a maximum symptom sub-scale score of 35, a maximum function sub-scale score of 40 giving a total maximum score of 75. A score of 47 or above has been shown to distinguish between psoriatic arthritis and non-psoriatic arthritis. This questionnaire is only intended to be a screening tool for psoriatic arthritis and does not replace a comprehensive musculoskeletal exam performed by a rheumatologist. This information will not be summarized.

Individual score to each of the 15 questions will be collected in the eCOA system. The sub-scale scores and total score will be derived in the analysis datasets.

8.2.2.9 Eight-Item Patient Health Questionnaire (PHQ-8)

The PHQ-8 is established as a valid diagnostic and severity measure for depressive disorders in large clinical studies. Each of the 8 questions is based on a 2-week recall and scored on a scale of 0 to 3 by a tick box as: 0=Not at All, 1=Several Days, 2=More than Half the Days, and 3=Nearly Every Day. A PHQ-8 score is derived by summing the scores for the 8 questions. The total PHQ-8 score ranges from 0-24. Scoring interpretation is as follows:

- 0-4 = no significant depressive symptoms
- 5-9 = mild depressive symptoms
- 10-14 = moderate depressive symptoms
- 15-19 = moderately severe depressive symptoms
- 20-24 = severe depressive symptoms

Response to each individual question is collected in the eCOA system. The total score will be derived in the analysis datasets.

8.2.2.10 electronic Columbia-Suicide Severity Rating Scale (eC-SSRS)

The electronic Columbia-Suicide Severity Rating Scale (eC-SSRS) is a computer-automated, patient-reported version of the C-SSRS instrument that defines 11 categories of suicidal ideation and behavior (SIB) events. Categories and definitions are provided in Appendix 23 of the protocol. The categories are as follows:

- Suicidal ideation
 1. Wish to be dead

- 2. Non-specific active suicidal thoughts
- 3. Active suicidal ideation with any methods without intent to act
- 4. Active suicidal ideation with some intent to act, without specific plan
- 5. Active suicidal ideation with specific plan and intent
- Suicidal behavior
 - 1. Preparatory acts or behavior
 - 2. Aborted attempt
 - 3. Interrupted attempt
 - 4. Actual attempt (Non-fatal)
 - 5. Completed suicide
- Self-injurious behavior, no suicidal intent

8.3 Missing, Unknown, or Partial Dates

Start Date		Stop Date						Missing /Ongoing
		Complete: yyyymmdd		Partial: yyyymm		Partial: yyyy		
Partial: yyyy mm	= 1 st dose yyyymm	<1 st dose	≥1 st dose	<1 st dose yyyymm	≥1 st dose yyyymm	<1 st dose yyyy	≥1 st dose yyyy	
	≠ 1 st dose yyyymm	2	1	n/a	1	n/a	1	1
Partial: yyyy	= 1 st dose yyyy		2	2	2	2	2	2
	≠ 1 st dose yyyy	3	1	3	1	n/a	1	1
	Missing		3		3	3	3	3
4	1	4	1	4	1	4	1	1

1 = Impute as the date of first dose

2 = Impute as the first of the month

3 = Impute as January 1 of the year

4 = Impute as January 1 of the stop year

Note: If the start date imputation leads to a start date that is after the stop date, then there is a data error and the start date is not imputed.

Imputation rules for partial or missing stop dates:

1. Initial imputation
 - a. For partial stop date "mmyyyy", impute the last of the month.
 - b. For partial stop date "yyyy", impute December 31 of the year.
 - c. For completely missing stop date, do not impute.

Sponsor: Bristol-Myers Squibb
Protocol no: IM011065

2. If the stop date imputation leads to a stop date that is after the death date, then impute the stop date as the death date.
3. If the stop date imputation leads to a stop date that is before the start date, then there is a data error and the stop date is not imputed.

Imputation rules for partial or missing death dates:

1. If death year and month are available but day is missing:
 - a. If "mmYYYY" for last contact date = "mmYYYY" for death date, set death date to the day after the last contact date.
 - b. If "mmYYYY" for last contact date < "mmYYYY" for death date, set death date to the first day of the death month.
 - c. If "mmYYYY" for last contact date > "mmYYYY" for death date, data error and do not impute.

If both month and day are missing for death date or a death date is totally missing, set death date to the day after the last contact date.

8.4 Study Periods

Period 1 = Week 0 to Week 16 visit date

Period 2 = Week 16 visit date +1 to Week 52 visit date

Follow-up = 4 week follow-up period

8.5 Day Ranges for Analysis Visits

Below are the day ranges for the analysis visit definitions. If more than one visit occurs within an analysis visit, then the visit that is closest to the target date should be used for analysis.

Period	Week	Target Day	Day Range
Baseline			Screening, 1
Period 1			
	Week 1	8	2, 11
	Week 2	15	12, 18
	Week 4	29	19, 43
	Week 8	57	44, 71
	Week 12	85	72, 99
	Week 16	113	100, Week 16 drug dispense date (if available) or use 127 if missing
Period 2			
	Week 20	141	1 st day after Week 16 drug dispense date, 155
	Week 24	169	156, 183
	Week 28	197	184, 211
	Week 32	225	212, 239
	Week 36	253	240, 267
	Week 40	281	268, 295
	Week 44	309	296, 323
	Week 48	337	324, 351
	Week 52	365	352, last visit date prior to Safety Follow-up

Sponsor: Bristol-Myers Squibb
Protocol no: IM011065

Period		
Week	Target Day	Day Range
Safety Follow-up	393	Safety Follow-up visit*

* The Safety Follow-up visit is identified from the SDTM visit label, and no windowing is applied for the creation of this analysis visit. Subjects who continue into the extension study are not expected to complete a safety follow-up.

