BSA = body surface area; CBC = complete blood count; DNA = deoxyribonucleic acid; ECG = electrocardiogram; eC-SSRS = electronic Columbia Suicide Severity Rating Scale; FSH = follicle stimulating hormone; HBV = hepatitis B virus; HBcAb = hepatitis B core antibody; HBsAb = hepatitis B surface antibody; HBsAg = hepatitis B surface antigen; HCV = hepatitis C virus; HIV = human immunodeficiency virus; hs-CRP = high-sensitivity C-reactive protein; IRT = interactive response technology; PASE = psoriatic arthritis screening and evaluation; PASI = Psoriasis Area and Severity Index; PE = physical examination; PHQ-8 = eight-item Patient Health Questionnaire; PsA = psoriatic arthritis; PSSD = Psoriasis Symptoms and Signs Diary; SAE = serious adverse event; sPGA = static Physician Global Assessment; T3 = triiodothyronine; T4 = thyroxine; TB = tuberculosis; TSH = thyroid stimulating hormone; V = visit; WOCP = women of childbearing potential.

Table 2: On-Treatment Procedural Outline (IM011065): Week 0 through Week 20

Procedure	Week 0 Baseline / D1 V2	Week 1 D8 (±3 d) V3	Week 2 D15 (±3 d) V4	Week 4 D29 (±3 d) V5	Week 8 D57 (±3 d) V6	Week 12 D85 (±3 d) V7	Week 16 D113 (±3 d) V8	Week 20 D141 (±3 d) V9	Notes
Clinical Efficacy/Health Outcomes									
DLQI	X	X	X	X	X	X	X		
sPGA	X	X	X	X	X	X	X		
PASI	X	X	X	X	X	X	X		
ss-PGA ^a	X	X	X	X	X	X			
PGA-F ^b	X			X	X	X			
Palmoplantar PGA ^c	X	X	X	X	X	X			

Table 2: On-Treatment Procedural Outline (IM011065): Week 0 through Week 20

Procedure	Week 0 Baseline / D1 V2	Week 1 D8 (±3 d) V3	Week 2 D15 (±3 d) V4	Week 4 D29 (±3 d) V5	Week 8 D57 (±3 d) V6	Week 12 D85 (±3 d) V7	Week 16 D113 (±3 d) V8	Week 20 D141 (±3 d) V9	Notes
PSSD									
Safety Assessments									
Complete PE	X						X		
Targeted PE		X	X	X	X	X		X	See Section 8.4.1
Body Weight	X						X		
Vital Signs	X	X	X	X	X	X	X	X	
ECG	X						X		
PHQ-8	X				X		X		See Section 8.4.6.1
eC-SSRS Assessment	X				X		X		Suicidal Ideation and Behavior since last visit
Adverse Event Assessment	X	X	X	X	X	X	X	X	
Concomitant Medication Use	X	X	X	X	X	X	X	X	
Laboratory Tests									
Hematology	X	X	X	X	X	X	X	X	
Lymphocytes Subsets (TBNK)	X				X		X		
Chemistry Panel	X	X	X	X	X	X	X	X	If CK >2.5 × ULN, reflex testing is required (see Section 8.4.5)
Hemoglobin A1C	X						X		
hs-CRP	X	X	X	X	X		X	X	

Table 2: On-Treatment Procedural Outline (IM011065): Week 0 through Week 20

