Procedure	Week 0 Baseline / D1 V2	Week 1 D8 (±3 d) V3	Week 2 D15 (±3 d) V4	Week 4 D29 (±3 d) V5	Week 8 D57 (±3 d) V6	Week 12 D85 (±3 d) V7	Week 16 D113 (±3 d) V8	Week 20 D141 (±3 d) V9	Notes
Fasting Lipid Panel	X				X		X		Subjects are required to fast for at least 10 hours prior to collection
Fasting Plasma Glucose	X				X		X		
Urinalysis	X						X		
Serum Immunoglobulin Levels (IgM, IgG, IgA, IgE)	X				X		X		
Pregnancy Test (Urine)	X			X	X	X	X	X	WOCBP Only
Study Treatment									
Randomize	X								
Dispense Study Treatment	X		X	X	X	X	X	X	
Study Treatment Compliance		X	X	X	X	X	X	X	See Section 6.6

CK = creatine kinase; D = Day; d = days; DLOI = Dermatology Life Quality Index; ECG = electrocardiogram; eC-SSRS = electronic Columbia Suicide Severity Rating Scale; [REDACTED] hs-CRP = high-sensitivity C-reactive protein; Ig = immunoglobulin; [REDACTED] PASI = Psoriasis Area and Severity Index; PE = physical examination; PGA = Physician's Global Assessment; PGA-F = Physician Global Assessment-Fingernails; PHQ-8 = eight-item Patient Health Questionnaire; [REDACTED] PSSD = Psoriasis Symptoms and Signs Diary; [REDACTED] sPGA = static Physician Global Assessment; ss-PGA = scalp-specific Physician's Global Assessment; TBNK = T, B, and natural killer cells; [REDACTED] Wk = Week; WOCP = women of childbearing potential.

Note: All visits ±3 Days

^a In subjects with scalp psoriasis at baseline

^b In subjects with nail psoriasis at baseline

^c In subjects with palmoplantar psoriasis at baseline

When multiple assessments are conducted at a single visit, the following is the order in which they should be done:

- 1) Health outcomes assessments
- 2) Safety assessments
- 3) Clinical efficacy assessments
- 4) Laboratory tests (eg, safety laboratory tests, [REDACTED])

On fasting days, safety assessments can be done first followed by blood draws, and then health outcomes and, finally, efficacy assessments. The dose of the drug on a visit day is to be taken after blood draws.

Table 3: **On-Treatment Procedural Outline (IM011065): Week 24 through Week 52**

Procedure	Week 24 D169 (± 3 d) V10	Week 28 D197 (± 3 d) V11	Week 32 D225 (± 3 d) V12	Week 36 D253 (± 3 d) V13	Week 40 D281 (± 3 d) V14	Week 44 D309 (± 3 d) V15	Week 48 D337 (± 3 d) V16	Week 52 ^a (or early DC) D365 (± 3 d) V17	Safety Follow-up ^b (Week 56) D393 (± 3 d) V18	Notes

Table 3: On-Treatment Procedural Outline (IM011065): Week 24 through Week 52

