Appendix 2 Summary of Efficacy Assessments

Assessment	Outcome Measure	Endpoint	Comparison	Analyses
sPGA (Sec 8.2.1.1)	sPGA 0/1 with at least 2 point improvement from baseline	W16	BMS vs. PBO	CMH, sensitivity analyses including tipping point analysis, multiple imputation (Sec 6.1.1.1-3)
		Baseline->W16 over time	BMS vs. PBO	Binary GEE and CMH by Week (Sec 6.1.5.1)
	sPGA 0	W16	BMS vs. PBO	CMH (Sec 6.1.2.1)
		Baseline->W16 over time	BMS vs. PBO	CMH by Week (Sec 6.1.5.1)
PASI (Sec 8.2.1.2)	PASI 75	W16	BMS vs. PBO	CMH, sensitivity analyses including tipping point analysis, multiple imputation (Sec 6.1.1.1-3)
		Baseline->Week 16 over time	BMS vs. PBO	Binary GEE and CMH by Week (Sec 6.1.5.1)
	PASI 90	W16	BMS vs. PBO	CMH (Sec 6.1.2.1)
		Baseline->W16 over time	BMS vs. PBO	CMH by Week (Sec 6.1.5.1)
	PASI 100	W16	BMS vs. PBO	CMH (Sec 6.1.2.1)
		Baseline->W16 over time	BMS vs. PBO	CMH by Week (Sec 6.1.5.1)
ss-PGA (Sec 8.2.1.4)	ss-PGA 0/1 among subjects with a baseline ss-PGA ≥ 3	W16	BMS vs. PBO	CMH (Sec 6.1.2.1)
		Baseline->W16 over time	BMS vs. PBO	CMH by Week (Sec 6.1.5.1)

Sponsor: Bristol-Myers Squibb
Protocol no: IM011065

PGA-F (Sec 8.2.1.6)	PGA-F 0/1 among subjects with a baseline PGA-F score ≥ 3	W16 Baseline->W16 over time	BMS vs. PBO	CMH (Sec 6.1.2.1) CMH by Week (Sec 6.1.5.1)
pp-PGA (Sec 8.2.1.8)	pp-PGA 0/1 among subjects with a baseline pp-PGA ≥ 3	W16 Baseline->W16 over time	BMS vs. PBO	CMH (Sec 6.1.2.1) CMH by Week (Sec 6.1.5.1)
PSSD / Symptom Score (Sec 8.2.2.1)	PSSD/Symptom 0 among subjects with baseline PSSD/symptom score ≥ 1	W16 Baseline->W16 over time	BMS vs. PBO	CMH (Sec 6.1.2.1) CMH by Week (Sec 6.1.5.1)

Sponsor: Bristol-Myers Squibb
Protocol no: IM011065

DLQI (Sec 8.2.2.2)	DLQI 0/1 among subjects with a baseline DLQI score ≥ 2	W16 Baseline->W16 over time	BMS vs. PBO	CMH (Sec 6.1.2.1) CMH by Week (Sec 6.1.5.1)
-----------------------	--	--------------------------------	-------------	--

Sponsor: Bristol-Myers Squibb
Protocol no: IM011065

PASE (Sec 8.2.2.8)	PASE	Screening only		No Analysis

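### SAP 8.5 ends the Week 2 window at Day 18 instead of the midpoint used at every other boundary, so a Week 2 visit on Days 19–22 is labelled Week 4 and normally dropped

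*SAP*

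**What the plan says.** SAP section 8.5 maps study days to analysis visits. Week 2 has target Day 15 and range 12–18; Week 4 has target Day 29 and range 19–43. Typical later rows read "Week 12 85 72, 99", "Week 24 169 156, 183" and "Week 48 337 324, 351" (visit, target day, first and last day). Where several visits fall in one window, "If more than one visit occurs within an analysis visit, then the visit that is closest to the target date should be used for analysis".

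The protocol's Schedule of Activities sets the visits at "Week 2 D15 (±3 d) V4" and "Week 4 D29 (±3 d) V5", with the general note "Note: All visits ±3 Days". The scheduling windows are therefore Days 12–18 for Week 2 and Days 26–32 for Week 4.

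SAP Appendix 2 uses the early visits in the analyses over time from baseline to Week 16. For sPGA 0/1 and PASI 75 the entry is "Binary GEE and CMH by Week (Sec 6.1.5.1"; for the other listed efficacy endpoints it is CMH by week alone. SAP 6.2.3 and 6.2.4 summarize laboratory and vital-sign data by time point.

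**The concern.** The windows in 8.5 are contiguous, so they are built to place off-schedule visits as well as punctual ones. From Week 4 on, each visit may be up to 14 days late and keep its label. Week 2 may be only 3 days late, although its next visit is also 14 days away.

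A Week 2 visit slightly beyond the ±3-day allowance therefore moves to Week 4. There it competes with the real Week 4 visit, and the closest-to-target rule normally removes it. The subject attended and was assessed, but the Week 2 tables show no record. If the Week 4 visit was missed, a reading from about three weeks stands in as the Week 4 value.

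The Week 2 visit collects sPGA, PASI, DLQI, scalp and palmoplantar assessments where applicable, vital signs, hematology, chemistry and hs-CRP (Protocol 1.3, Table 2). What is at stake is the completeness of the early time course, which bears on the secondary objective of superiority over the first 16 weeks.

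**Working it through.** **Inputs.** Target days and ranges come from SAP 8.5, scheduling windows from Protocol 1.3, and the sample size of about 219 from Protocol 4.2.

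**Step 1: the rule the table follows.** For adjacent targets T1 and T2, the midpoint is (T1 + T2)/2. Compare it with the stated last day of the earlier window.

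| Boundary | Midpoint | Stated last day |
|---|---|---|
| Weeks 1/2 | (8 + 15)/2 = 11.5 | 11 |
| **Weeks 2/4** | **(15 + 29)/2 = 22** | **18** |
| Weeks 4/8 | (29 + 57)/2 = 43 | 43 |
| Weeks 8/12 | (57 + 85)/2 = 71 | 71 |
| Weeks 12/16 | (85 + 113)/2 = 99 | 99 |
| Weeks 16/20 | (113 + 141)/2 = 127 | 127 (fallback if the dispense date is missing) |
| Weeks 20/24 | (141 + 169)/2 = 155 | 155 |
| Weeks 24/28 | (169 + 197)/2 = 183 | 183 |

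The next six boundaries, up to Weeks 48/52, are 211, 239, 267, 295, 323 and 351, and all equal their midpoints. In total 13 of 14 boundaries agree, counting the Week 16 fallback. Where the midpoint is a whole day, that day goes to the earlier visit. Only Weeks 2/4 departs.

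**Step 2: does the protocol window explain it?** Day 15 ± 3 gives 12–18, which reproduces the Week 2 row. Day 29 ± 3 gives 26–32, which does not reproduce 19–43. Neither rule produces both rows.

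**Step 3: where a late Week 2 visit goes.**

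| Day of Week 2 visit | Distance to Day 15 | Distance to Day 29 | Label in SAP | Real Week 4 visit is kept if held by |
|---|---|---|---|---|
| 19 | 4 | 10 | Week 4 | Day 38 |
| 20 | 5 | 9 | Week 4 | Day 37 |
| 21 | 6 | 8 | Week 4 | Day 36 |
| 22 | 7 | 7 | Week 4 | Day 35 |

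A Week 4 visit on Days 26–32 is at most 3 days from target, so it always wins. The late Week 2 record is then unused, and Week 2 is empty unless another visit falls on Days 12–18. If the Week 4 visit is absent, or held from Day 40, 39, 38 or 37 onward respectively, the Week 2 visit becomes the Week 4 value.

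**Step 4: how many subjects.** The documents give no distribution of visit days. If 1% to 5% of Week 2 visits fall on Days 19–22 (an assumption), 0.01 × 219 = 2.2 and 0.05 × 219 = 11.0, so about 2 to 11 subjects.

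**The case against.** The SAP never states a midpoint rule; it is inferred from the table. The Week 2 range is the protocol's scheduling window, symmetric about target, and every punctual Week 2 visit is classified correctly. Keeping a three-week reading out of Week 2 can be defended. This stands as a possible intention, but it does not explain why Week 4 alone opens at Day 19, and the SAP gives no reason.

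Day 22 is a tie, so only Days 19–21 are nearer Week 2. That stands; Day 22 moves only by the table's own tie convention. The missed-Week-4 consequence is also mild by the table's standards: Day 19 is 10 days before the Week 4 target, while the Week 8 and later windows accept readings 13 days early.

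A reader might infer more than the documents support:

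- **That affected subjects become Week 2 non-responders.** The NRI rules visible in the SAP (6.1.1.1 and 6.1.2) cover Weeks 16 and 52. The by-week CMH refers to 6.1.5.1, whose current text cannot be seen. Protocol 9.4.2.1 applies NRI to binary secondary endpoints generally, so imputation at Week 2 is possible but not shown.
- **That the GEE result is distorted.** The only visible description, in the SAP document history, reports Week 16 differences without imputation. A lost Week 2 record could act there only indirectly. The same is true of the multiple-imputation sensitivity analysis, which conditions on earlier data.
- **That safety signals are lost.** Adverse events are assigned by start date (6.2.1). Worst post-baseline values rest on observed values (8.1), with no stated restriction to the windowed record. Only by-time-point tables are exposed.

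**Conclusion.** The point holds as a minor inconsistency. One boundary out of 14 departs from the table's pattern without a stated reason. As a result, completed Week 2 visits on Days 19–21, and the equidistant Day 22, are labelled Week 4 and dropped whenever Week 4 is on schedule.

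The reach is limited to by-visit Week 2 and Week 4 efficacy summaries, the by-week CMH tests and the by-time-point safety tables. SAP 6.1.3 makes no multiplicity adjustment for other time points, so p-values there are nominal. It would be wrong to read this as a threat to the trial's conclusions: both coprimary endpoints and all seven endpoints in the testing hierarchy are assessed at Week 16, and their NRI and CMH analyses do not use the Week 2 window.

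The arithmetic on the windows is exact. The number of subjects is not known, and the range of 2 to 11 rests wholly on the assumed 1–5%.

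**What to change.** In SAP 8.5, set Week 2 to Days 12–22 and Week 4 to Days 23–43. If the narrow Week 2 window is intended, say why in one sentence and state how late Week 2 visits are handled. Either is best settled before treatment codes are released for the Week 16 analysis.

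The cost is two numbers in a table and the matching derivation. There is a small downside. A Week 4 visit held 7–10 days early (29 − 10 = 19 to 29 − 7 = 22) would fall in the Week 2 window, lose to a punctual Week 2 visit and leave Week 4 empty; the present table keeps it. That is less likely than a Week 2 visit 1–4 days beyond its allowance. The Week 2 window would also become asymmetric, from 3 days before target to 7 days after, though still narrower than the later windows, which run from 13 days before to 14 after.

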10.0 Document History

Version Number	Version Date	Summary of Changes
1.0 - Original Document	06-Apr-2021	Not applicable
2.0 – Amendment 01	22-Jul-2021	Revisions provided below.

Revisions for Amendment 01: Key additions and revisions in this amendment are specified below. Minor clarifications or typographical and formatting changes were made but are not repeated here. Additions are noted by bold text. Removals are noted by strikethrough.

SAP Section	Revised Text	Rationale for Change

6.1.4	
Subgroup analyses will be performed on the coprimary endpoints using the FAS. The primary imputation method will be applied for these analyses. The CMH test using the stratification factors from IRT will be the analysis method used. The following subgroups will be considered:
 
• Region (Greater China, Non-Greater China)• Country (Mainland China, Taiwan, South Korea)• Sex (male, female)• Age group (<65 y, ≥65 y)• Body weight (<90 kg, ≥90 kg)• Prior biologic use (yes, no) – from case report form• Prior systemic treatment of psoriasis (Yes/No)• Prior phototherapy (Yes/No)• sPGA (3, 4)• PASI score (≤20, >20)• BSA involvement (10-20, >20)	Key analyses will be repeated for Greater China under country specific analysis.
-------	--	--

Sponsor: Bristol-Myers Squibb
Protocol no: IM011065

	
Duration of disease (< 10 y, \geq 10 y) Age at disease onset (<18, 18-39, \geq40)	
6.1.5.1	
Binary Repeated Measures Analysis
 
Additionally, longitudinal analyses over time (through Week 16) of binary repeated measures data will be performed for the primary and key secondary endpoints. Generalized estimation equation methodology will be used to perform the longitudinal analysis. Treatment group, stratification factors from IRT, visit, and treatment-by-visit interaction will be included in the model as fixed effects. Treatment differences in proportions for Week 16 and the 95% CI for the treatment difference will be provided. No imputation methods will be used for this analysis. Any p-values that are provided will be considered nominal.
	GEE models provided minimal value in other protocols and will applied only to primary endpoints.
6.1.5.2	
Mixed Model Repeated Measures (MMRM)
 
Additionally, for key secondary continuous change from baseline endpoints assessed over time (through Week 16), an MMRM analysis will be used. Treatment group, stratification factors from IRT, visit, and treatment by visit interaction will be included in the model as fixed effects. Baseline value of the specified endpoint will be added to the model as a covariate, if applicable. An unstructured covariance structure will be used for modeling the data over time. Kenward and Roger's (1997) approach will be used to approximate the denominator degrees of freedom. The adjusted LS means and treatment differences based on LS means will be provided along with the corresponding 95% CIs for comparisons between BMS 986165 and placebo. Data is assumed to be missing at random. No imputation methods will be used for this analysis. Any p-values that are provided will be considered nominal.
	This section is removed since key secondary endpoints do not include any continuous parameters.
6.2.3	Laboratory parameters will be summarized using the International System (SI) of Units and US conventional units.	Only SI units will be presented since study

Sponsor: Bristol-Myers Squibb
Protocol no: IM011065

	
Data will be summarized by time point, as applicable. The following summaries will be provided for each parameter:
 
• Absolute, change from baseline values for continuous parameters• Number and percentage of subjects for the following:
○ Maximum postbaseline CTCAE grade for each applicable laboratory parameter○ Shifts from baseline based on maximum postbaseline CTCAE grade• Drug-induced Liver Injury (DILI) and Hy's Law summaries	is conducted in Mainland China, Taiwan, and South Korea.
6.3.2	
Demographic and baseline characteristics will be summarized by treatment group for the FAS. Demographic characteristics include the following:
 
• Sex• Race• Ethnicity• Age (in years, at time of signing informed consent) and age category (<65 vs ≥65)• Weight (in kg, at baseline) and weight category (<90 kg vs ≥90 kg)• Body mass index (BMI in kg/m², at baseline)• Region (Greater China, Non-Greater China)• Country (Mainland China, Taiwan, South Korea)	Key analyses will be repeated for Greater China under country specific analysis.

Sponsor: Bristol-Myers Squibb
Protocol no: IM011065

	
• Prior biologic use for psoriasis, psoriatic arthritis and other inflammatory diseases only (yes, no)• Reason for discontinuation of prior biologic use• Prior systemic treatment use (yes/no)• Prior phototherapy use (yes/no)• Stratification factors obtained from IRT: country (mainland China, non-Mainland China) and prior biologic use• Stratification factors obtained from database: country (mainland China, non-Mainland China) and prior biologic use• sPGA (3, 4)• PASI score (≤ 20, > 20)• BSA involvement (10-20, > 20)• Duration of disease (< 10 y, ≥ 10 y)• Age at disease onset (< 18, 18-39, ≥ 40)• Additional demographics or baseline data may be added to summary tables.	
6.6	Country or region specific analyses may take place to support regional health authorities submissions. In general these would consist of repeating a subset of the analyses described in this SAP for subjects from a specific country, which would potentially be used for evaluation of consistency between the country and the overall population.	Regulatory requirement for certification of sites within Taiwan.

Sponsor: Bristol-Myers Squibb
Protocol no: IM011065

	
Unless otherwise noted, the same analysis methods will be used as for the global population. Also, unless otherwise noted, no formal hypothesis testing will be performed and descriptive summary statistics and estimates will be provided for evaluation of consistency of the population. No adjustment for multiplicity will be made. Stratification factors may or may not be used in analyses as appropriate, taking into account the size of the population.
 
Country specific analysis will be performed for the Greater China subgroup. This population contains subjects that are Chinese by race and enrolled at sites within mainland China and National Medical Products Administration certified sites within Taiwan.
	
--	---	--

